## 7.4.2 Secondary Outcome Analyses

Similar analyses will be conducted for binary secondary outcomes (continues variables will be categorized into binary variable), including frequency of syphilis testing, frequency of HIV testing (among those with previous HIV testing), condomless sex, community engagement, awareness of HIV status, empowerment and others. In addition, since four cities will implement more intensive in-person events to promote engagement (Guangzhou, Shenzhen, Qingdao, and Jinan) during intervention development, sub-analysis will be conducted to evaluate the potential effect of in-person events to promote HIV testing and other secondary outcomes among Chinese MSM. In addition, secondary analysis will investigate an interaction effect between intervention and community engagement (both for engagement during the intervention development stage and engagement during the intervention implementation stage, at personal level).

## 7.4.3 Sub-Analyses

Sub-analysis will also be conducted to compare the effect of the intervention in participants with different age (less than 30 versus 30 or older), and to compare two delivery methods for individual-level intervention: WeChat message vs. SMS text message.

## 8 Ethical approval

IRB approval will be obtained from the following institutional ethical review boards prior to study enrolment: Guangdong Provincial Center for Skin Diseases and STI Control, University of North Carolina at Chapel Hill, and University of California San Francisco.

## 9 Trial status

At the time of this draft, intervention development and participant recruitment have initiated. Study outcomes, data cleaning, and analysis are pending. The study is registered in the Clinical Trials.gov database (NCT02796963).

# 10 Appendix 1. Secondary outcomes measured as part of this RCT.

Secondary Outcome	Definition	
Incremental cost	Incremental cost, defined as the cost associated with	
	respective interventions (development, start-up,	
	implementation, condom use, intervention per individual	
	who reported no sex or sex with a condom during the	
	follow-up period.)	
Condom use	Frequency of men, defined as the number of men who	
	reported increased condom use (in anal, vaginal, and/or	
	oral sex with either male and female sex partners)	
	comparing pre-intervention and post-intervention values	
HIV testing social	Frequency of men, defined as number of men who report	
norms 	higher levels of social norms when comparing their pre-	
	intervention and post-intervention HIV testing norms	
HIV testing self-	Frequency of men, defined as number of men who had an	
efficacy 	increase in HIV testing self-efficacy when comparing	
	their pre-intervention and post-intervention self-efficacy	
Community	Frequency of men, defined as an increase in closer	
engagement/ MSM	affiliation with the MSM community (i.e., tongzhi circle,	
community affiliation	gay online networks or groups) when comparing their pre-	
2 55	intervention and post-intervention engagement	
Campaign engagement	Frequency of men, defined as number of men who had an	
1000	increase in taking part in the HIV testing campaign when	
	comparing their pre-intervention and post-intervention	
	engagement	
HIV self-testing	Frequency of men, defined as the number of men who	
	reported being self-tested for HIV during the previous	
	three months	
Anticipated HIV	Frequency of men, defined as number of men who report	
stigma 	anticipated HIV stigma when comparing their pre-	
	intervention and post-intervention	
Syphilis testing	Frequency of men, defined as the number of men who	
	reported being tested for syphilis (excluding HIV) during	
	the previous three months	
Weibo engagement	Frequency of men, defined as the number of men who	
	reported using Weibo in the past three months to give or	
	receive information about HIV testing comparing their	
	pre-intervention and post-intervention engagement	
	(Except the intervention delivered by SESH)	
Wechat engagement	Frequency of men, defined as the number of men who	
	reported using Wechat in the past three months to give or	
	receive information about HIV testing comparing their	
	pre-intervention and post-intervention engagement	
	(Except the intervention delivered by SESH)	
QQ engagement	Frequency of men, defined as the number of men who	
	reported using QQ in the past three months to give or	
	receive information about HIV testing comparing their	

	pre-intervention and post-intervention engagement (Except the intervention delivered by SESH)
Mobile app engagement	Frequency of men, defined as the number of men who reported using mobile apps in the past three months to give or receive information about HIV testing comparing their pre-intervention and post-intervention engagement

 HIV testing social norms will be measured using six survey items that are each on a five point Likert scale. Increased HIV testing social norms will be defined as having an increase from baseline in any two of these six survey items and dichotomized accordingly (social norm change will be categorized into three groups: increased, stable and decreased social norm). The HIV testing social norm outcome will be assessed in the entire group as well as the subgroup of men who were referred by their friends. This is adapted from Pettifor, A., MacPhail, C., Suchindran, S, & Delany-Moretlwe, S. (2015). Factors associated with HIV testing among public sector clinic attendees in Johanesburg, South Africa. AIDS and Behavior, 14, 913-921.

 Self-efficacy will be measured using six survey items that are each on a five point Likert scale. Increased self-efficacy will be defined as having an increase from baseline in any two of these seven survey items and dichotomized accordingly (self-efficacy change will be categorized into three groups: increased, stable and decreased self-efficacy). This is adapted from Gu, J., Lau, J. T. F., & Tsui, H. (2011). Psychological factors in association with uptake of voluntary counselling and testing for HIV among men who have sex with men in Hong Kong. Public Health, 125, 275-282.

 The Anticipated HIV Stigma will be assessed using 7 survey items that are each on a four point Likert scale. Reduced anticipated HIV stigma will be defined as having a decrease from baseline in the mean score (Continuous variable). This is adapted from Golub, S. A. & Gamarel, K. E. (2013). The impact of anticipated HIV stigma on delays in HIV testing behaviors; Findings from a community-based sample of men who have sex with men and transgender women in New York City. AIDS Patient Care and STDs, 27(11), 621-627.

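### The any-two-items rule for social norms and self-efficacy can count a man whose score fell as improved, and it leaves the item count and the three change groups unsettled

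*Combined protocol and SAP*

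**What the plan says.** The Appendix 1 table defines social norms and self-efficacy as counts of men whose level is higher after the intervention than before it. The footnotes turn this into item rules.

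- **Social norms (footnote 1).** The instrument: "HIV testing social norms will be measured using six survey items that are each on a five point Likert scale". The rule: "Increased HIV testing social norms will be defined as having an increase from baseline in any two of these six survey items and dichotomized accordingly". The same sentence adds that "social norm change will be categorized into three groups: increased, stable and decreased social norm".
- **Self-efficacy (footnote 2).** The instrument: "Self-efficacy will be measured using six survey items that are each on a five point Likert scale". The rule: "Increased self-efficacy will be defined as having an increase from baseline in any two of these seven survey items and dichotomized accordingly". It also names three change groups.
- **Anticipated stigma (footnote 3).** Improvement is "having a decrease from baseline in the mean score (Continuous variable").
- **Analysis (section 7.4.2).** Secondary outcomes are handled like the primary outcome, as binary variables: "continues variables will be categorized into binary variable".

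No section sets a minimum rise, a net-score condition, or a rule for the stable and decreased groups.

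**The concern.** The rule looks only at items that go up, while the outcome it is meant to express is a higher level on the scale. The two can disagree in direction for the same man. Social norms are named in Hypothesis 2 (section 3.2), and footnote 1 repeats the outcome in the subgroup of men referred by friends, so a reported proportion increased would be read as benefit.

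Two gaps in wording add to this. Footnote 2 does not agree with itself on how many items the rule runs over. Both footnotes call for a dichotomy and for three groups, without saying where a man with some rises and some falls belongs. Two analysts could report different groups from the same data.

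**Working it through.** The plan gives no responder rate, item reliability or effect size for these outcomes, so there is no figure of its own to reproduce.

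**1. Direction (no assumption needed).** Take six items scored 1 to 5. Two items go from 1 to 2 and four go from 5 to 1.
- Baseline total: 2×1 + 4×5 = 22.
- Follow-up total: 2×2 + 4×1 = 8.
- Two items rose, so the man is increased although his total fell by 14.

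**2. Responder rate from noise alone (assumed inputs).** Let p be the chance that one item rises with no true change, with items independent. For k items, P(increased) = 1 − (1−p)^k − k·p·(1−p)^(k−1). At k = 6 and p = 0.20 this is 1 − 0.262 − 0.393 = 0.345.

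| p | k = 6 | k = 7 |
|---|---|---|
| 0.05 | 3.3% | 4.4% |
| 0.10 | 11.4% | 15.0% |
| 0.15 | 22.4% | 28.3% |
| 0.20 | 34.5% | 42.3% |
| 0.25 | 46.6% | 55.5% |

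The second column shows what the six/seven conflict is worth: about 8 percentage points at p = 0.20.

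**3. Falls among the increased.** Let each item rise with chance p, fall with chance p, and otherwise stay the same. Count men with at least two rises (k = 6), as a share of increased men.

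| p | more falls than rises | equal falls and rises | together |
|---|---|---|---|
| 0.10 | 0.4% | 5.1% | 5.5% |
| 0.20 | 3.6% | 15.4% | 19.0% |
| 0.25 | 7.1% | 19.9% | 27.0% |

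With one-point moves, more falls than rises means a lower total and equal numbers mean no change. As a share of all men, more falls than rises is 0.345 × 0.036 = 1.2% at p = 0.20 and 0.466 × 0.071 = 3.3% at p = 0.25.

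**4. Group overlap.** The plan gives no decreased rule. If it mirrored the increased rule, men with at least two rises and at least two falls would meet both: 7.8% of men at p = 0.20 and 15.9% at p = 0.25 (k = 6).

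**5. Simulated five-point items, no true change.** Assumed item retest reliability was 0.5, 0.7 or 0.85, and inter-item correlation 0.2 or 0.5. On six items, 35-65% of men were increased, and the total had fallen in 6-22% of those. With reliability 0.7 and noise almost wholly shared across items, the increased rate dropped from 56% to 39%, and the share whose total fell from 16% to about zero.

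**6. Precision.** Efficiency of the rule relative to the mean score, in three sets of simulations with different assumed loadings and stability, was 0.35-0.46, 0.43-0.61 and 0.40-0.58.

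**The case against.** - **The noise rate is assumed.** This stands. Nothing in the documents shows how often an item shifts on retest. If chance rises occur in 5% of men or fewer, the noise-only rate is about 3%.
- **Noise is present in both conditions.** This stands. A reader might infer that a high no-change rate would create an apparent benefit. The documents do not support that: section 7.4.1 compares intervention with control periods and adjusts for time, and section 7.4.2 carries this over to secondary outcomes.
- **Few increased men are net losers.** This stands in part. A reader might take the 19-27% in the working as men whose score fell, but most of that is ties. The share with more falls than rises is 4-7%, and near zero if noise is shared. The direction error in step 1 remains possible under the stated rule.
- **The dichotomy is usable as it is.** Increased versus not increased is exclusive, and the self-efficacy threshold is two items. That is correct, so the overlap in step 4 concerns the three-group report and rests on a mirrored rule that the plan does not state. The missing group rule and the six/seven conflict still need repair.
- **Footnote 3 does not already commit the plan to a continuous analysis.** Correct: stigma is still listed as a count of men, and section 7.4.2 dichotomises. Footnote 3 supports only judging direction on the mean score.
- **A mean difference changes the declared outcome.** This is a real cost, and it is named in the fix.

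**Conclusion.** The concern holds in a limited form. From the wording alone, footnotes 1 and 2 allow a man whose total fell to be counted as improved, contrary to the outcome that the Appendix 1 table describes. Footnote 2 conflicts with itself on the number of items, and the three groups lack an exclusive rule. None of this depends on an assumption.

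The size does. With independent items and no true change, the noise-only rate on six items runs from 3% to 47% as the chance of an item rising goes from 5% to 25%. The consequence is misclassification, attenuation and lost precision, with efficiency of about 0.35 to 0.6 of the mean score in simulation. A reader might conclude that more than half the information is always lost; the upper end of that range does not bear this out. Only these two secondary outcomes are affected; the primary analysis is untouched.

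**What to change.** 1. In Appendix 1, score social norms and self-efficacy as the mean of their items at each survey. Analyse that score in a linear mixed model with the fixed and random effects of section 7.4.1.
2. In section 7.4.2, exempt these two scales from conversion to binary variables.
3. In footnote 2, reconcile six and seven with the instrument used.
4. If a count of men is still reported, make it descriptive and define the three groups by the change in mean score, so that they are exclusive and a net fall cannot count as increased. This does not remove the noise: with no true change, any rise in total score still labels about 37-44% of men increased in the simulations of step 5 (six or seven items).

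The cost is wording only. No new data are needed, and section 9 says that outcomes and analysis are still pending. The small downside is that the main result becomes a mean difference rather than a count of men.
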